5.2 Exclusion Criteria

Specific exclusion criteria are:

1. Prior treatment with investigational therapy.

Participants may not have had any treatments with investigational therapy within the 28 days prior to initiation of study treatment.

2. Prior radiation therapy

Participants may not have had radiation therapy within 2 weeks prior to initiation of study treatment. Participants may not have had previous radiotherapy to 25% or more of the bone marrow.

3. Prior Therapy

Participants may not have had systemic chemotherapy within 14 days or 5 half-lives of the drug (whichever is longer) prior to initiation of study treatment.

In addition, the following prior treatment is not allowed during **Phase 1** of the study:

- Receptor tyrosine kinase inhibitors targeting MAP kinase pathway;

Columbia University Irving Medical Center
Herbert Irving Comprehensive Cancer Center
AAAS4165_Version Date: 07/07/2021

- Any pharmacological agents inhibiting the autophagy pathway.

In addition, the following prior treatment is not allowed during **Phase 2** of the study:

- T-cell co-stimulating agents or immune checkpoint blockade therapies, including but not limited to anti-CTLA-4, anti-PD-1, and anti-PD-L1 therapeutic antibodies;
- Receptor tyrosine kinase inhibitors targeting MAP kinase pathway;
- Any pharmacological agents inhibiting the autophagy pathway.

4. Adverse events from prior anti-cancer therapy

Participants may not initiate treatment if they have adverse events from prior anti-cancer therapy that have not resolved to Grade ≤ 1 or better, with the exception of Grade ≤ 2 peripheral neuropathy or any grade alopecia.

5. Patients currently receiving any other investigational agents
6. Concomitant treatment with other anti-neoplastic agents (hormone therapy acceptable)
7. Uncontrolled pleural effusion, pericardial effusion, or ascites
8. Patients with symptomatic brain metastases

Subjects with untreated brain metastasis ≤ 1 cm can be considered eligible if deemed asymptomatic by the investigator upon consultation with the medical monitor, and do not require immediate radiation or steroids. Subjects with brain metastasis that is treated and stable for 1 month may be considered eligible if they are asymptomatic and on stable dose of steroids, or if they do not require steroids following successful local therapy.

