9. Uncontrolled hypercalcemia (ionized calcium > 1.5 mmol/L, calcium > 12 mg/dL, or corrected serum calcium $>$ ULN) or symptomatic hypercalcemia requiring continued use of bisphosphonate therapy.
10. Recent major surgery or significant traumatic injury

Participants may not have undergone major surgery or experienced significant traumatic injury within 14 days prior to initiating study treatment, or be recovering from a procedure related to adverse events of \leq Grade 1.

11. Active or history of autoimmune disease or immune deficiency

Includes, but is not limited to, myasthenia gravis, myositis, autoimmune hepatitis, systemic lupus erythematosus, rheumatoid arthritis, inflammatory bowel disease, antiphospholipid antibody syndrome, Wegener granulomatosis, Sjögren's syndrome, Guillain-Barré syndrome, or multiple sclerosis, with the following exceptions:

- Patients with a history of autoimmune-related hypothyroidism who are on stable thyroid-replacement hormone are eligible for the study.
- Patients with controlled Type 1 diabetes mellitus who are on a stable insulin regimen

Columbia University Irving Medical Center
Herbert Irving Comprehensive Cancer Center
AAAS4165_Version Date: 07/07/2021

are eligible for the study.

- Patients with eczema, psoriasis, lichen simplex chronicus, or vitiligo with dermatologic manifestations only (e.g., patients with psoriatic arthritis are excluded) are eligible for the study provided all of following conditions are met:
 - Rash must cover <10% of body surface area;
 - Disease is well-controlled at baseline and requires only low-potency topical corticosteroids;
 - No occurrence of acute exacerbations of the underlying condition requiring psoralen plus ultraviolet A radiation, methotrexate, retinoids, biologic agents, oral calcineurin inhibitors, or high-potency or oral corticosteroids within the previous 12 months.

12. History of idiopathic pulmonary fibrosis, interstitial lung disease, organizing pneumonia (e.g., bronchiolitis obliterans), drug-induced pneumonitis, or idiopathic pneumonitis, or evidence of active pneumonitis on screening chest computed tomography scan [history of radiation pneumonitis in the radiation field (fibrosis) is permitted].

13. Positive for HIV at screening or any time prior to screening

Patients without prior positive HIV test result will undergo an HIV test at screening, unless not permitted under local regulations.

14. Active Hepatitis B virus (HBV) infection (chronic or acute)

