23. Grade \geq 3 hemorrhage or bleeding event within 28 days prior to initiation of study treatment

24. Prior autologous stem cell, allogeneic stem cell, or solid organ transplantation

25. History of malignancy

Patient may not have a history of malignancy other than PDA within 2 years prior to screening, with the exception of those with a negligible risk of metastasis or death (e.g., 5-year overall survival of $> 90\%$), such as adequately treated carcinoma *in situ* of the cervix, non-melanoma skin carcinoma, localized prostate cancer, ductal carcinoma *in situ*, or Stage I uterine cancer.

26. Recent vaccination

Patients may not have been treated with a live, attenuated vaccine within 4 weeks prior to initiation of study treatment, or anticipate the need for such a vaccine during treatment with atezolizumab or within 5 months after the last dose of atezolizumab.

27. History of severe allergic anaphylactic reactions to chimeric or humanized antibodies or fusion proteins

28. Known allergy or hypersensitivity to 4-aminoquinoline compounds or any of the study drug excipients

29. Recent immunosuppressive treatment

Patients may not have been treated with systemic immunosuppressive medication (including, but not limited to, corticosteroids, cyclophosphamide, azathioprine, methotrexate, thalidomide, and anti-tumor necrosis factor alpha agents) within 2 weeks prior to initiation of study treatment, or

Columbia University Irving Medical Center
Herbert Irving Comprehensive Cancer Center
AAAS4165_Version Date: 07/07/2021

anticipate the need for systemic immunosuppressive medication during the course of the study, with the following exceptions:

- Patients who received mineralocorticoids (e.g., fludrocortisone), corticosteroids for chronic obstructive pulmonary disease or asthma, or low-dose corticosteroids for orthostatic hypotension or adrenal insufficiency are eligible for the study if receiving equivalent to < 10mg of prednisone daily.
- Patients who received a one-time pulse dose of systemic immunosuppressant medication are eligible for the study after approval from the Principal Investigator.

30. Inability to swallow medication or malabsorption condition that would alter the absorption of orally administered medications

31. History of retinal pathology

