Patients may not have a history of or evidence of retinal pathology on ophthalmologic examination that is considered a risk factor for neurosensory retinal detachment, central serous chorioretinopathy, retinal vein occlusion (RVO), or neovascular macular degeneration. Specifically, patients will be excluded from study participation if they currently are known to have any risk factors for RVO, including:

- Glaucoma with intraocular pressure ≥ 21 mmHg;
- Grade ≥ 2 serum cholesterol;
- Grade ≥ 2 hypertriglyceridemia;
- Grade ≥ 2 uncontrolled hypertension (patients with a history of hypertension controlled with anti-hypertensive medication to Grade ≤ 1 are eligible).

32. Pregnancy

Pregnant women are excluded from this study because there is an unknown, but potential risk for AEs in nursing infants secondary to treatment of the mother with these agents; breastfeeding should be discontinued.

33. Other contraindicated conditions

Any other disease, metabolic dysfunction, physical examination finding, or clinical laboratory finding that contraindicates the use of an investigational drug, may affect the interpretation of the results, or may render the patient at high risk from treatment complications in the opinion of the treating investigator.

34. Concomitant strong CYP3A4 inhibitors and inducers

Refer to list of common CYP3A4 inhibitors and inducers (Appendix 2). These include anticonvulsants, mycin antimicrobials, and antiretrovirals. Some common examples include inhibitors, such as erythromycin, fluoxetine, gemfibrozil, and inducers, such as rifampicin, carbamazepine, phenytoin, efavirenz, and nevirapine. Concomitant treatment is permitted if the

Columbia University Irving Medical Center
Herbert Irving Comprehensive Cancer Center
AAAS4165_Version Date: 07/07/2021

medication is not expected to interfere with the evaluation of safety or efficacy of the study drug. During the study, if the use of any concomitant treatment becomes necessary (e.g., for treatment of an adverse event), the treatment must be recorded on the eCRF, including the reason for treatment, generic name of the drug, dosage, route, and start and stop dates of administration.

35. Uncontrolled psoriasis, porphyria, proximal myopathy or neuropathy

36. Severe depression

Subjects hospitalized for depression within the past 2 years, or who have prior suicidal attempts will be excluded.

37. Gluocose-6-phosphate dehydrogenase (G-6-PD) deficiency

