10. Fresh core tumor biopsy will be performed: (1) within 14 days of starting therapy but at least three days prior to starting therapy; (2) Cycle 1 week 3 (day 15-21); and (3) If the patient allows, at progression (within 4 days of discontinuation of therapy).
11. TSH, free T4, and AM cortisol will be assessed at screening, Day 1 of each cycle starting at C2, at end of study, and as clinically appropriate.
12. At screening, patients without a prior positive HIV test result will undergo an HIV test, unless not permitted per local regulations. Patients will also be tested for HBsAg, HBsAb, total HBcAb, and HCV antibody. If a patient has a negative HBsAg test and a positive total HBcAb test at screening, an HBV DNA test should be performed. If a patient has a positive HCV antibody test at screening, an HCV RNA test must also be performed to determine if the patient has an active HCV infection.
13. For women of child-bearing potential, a screening serum pregnancy test must be negative within 7 days of Day 1 of Cycle 1.
14. Peripheral blood mononuclear cells will be collected during screening, cycle 1 day 15, cycle 3 day 1, every eight weeks (+ 7 days), and at End-of-Service visit.
15. CT scan with contrast of the chest, abdomen, pelvis or CT chest and MRI of abdomen/pelvis, PET/CT, or appropriate imaging of disease site to assess tumor status will be performed. Imaging should be performed at the designated time for tumor assessment +/- 7 days. End of study needs not be performed if patient has radiological evidence confirming progression, but needs to be performed if patient coming off study for other reasons, except due to fatality.
Phase 1 –Imaging to be performed every 8 weeks (+ 7 days)
Phase 2 –Pancreas adenocarcinoma –Imaging to be performed every 8 weeks (+ 7 days)
Colorectal adenocarcinoma – Imaging to be performed every 12 weeks (+ 7 days)
Histology agnostic adenocarcinoma – Imaging to be performed every 8 weeks (+ 7 days)
16. The initial dose of atezolizumab will be delivered over 60 (+/- 15) minutes. Subsequent infusions will be delivered over 30 (+/-10) minutes if the previous infusion was tolerated without infusion-associated adverse events, or 60 (+/- 15) minutes if the patient experienced an infusion-associated adverse event with the previous infusion.
17. For pharmacokinetic (PK) analysis, whole blood for hydroxychloroquine and plasma for cobimetinib will be obtained on –
Cycle 1 Day 1 - Pre-morning dose, 1, 2, and 4 hours post-morning dose.

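### Exclusion 10 is reversed as written: its procedure limb excludes patients with residual events of Grade 1 or lower and does not catch those with Grade 2 or higher.

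*Combined protocol and SAP*

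**What the plan says.** Section 5.2, item 10, headed as recent major surgery or significant traumatic injury, is a single sentence with two limbs under one prohibition.

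- First limb: "Participants may not have undergone major surgery or experienced significant traumatic injury within 14 days prior to initiating study treatment".
- Second limb: "or be recovering from a procedure related to adverse events of" Grade 1 or lower. The sign printed before Grade 1 is ≤.

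Three other items in section 5.2 help in reading it.

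- Item 4 bars the start of treatment in patients with "adverse events from prior anti-cancer therapy that have not resolved to Grade ≤ 1 or better", except peripheral neuropathy up to Grade 2 and alopecia of any grade.
- Item 23 bars a Grade ≥ 3 "hemorrhage or bleeding event within 28 days prior to initiation of study treatment".
- Item 33 bars any other condition or finding that, among other grounds, "may render the patient at high risk from treatment complications in the opinion of the treating investigator".

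The opening of section 5 makes every criterion binding for eligibility. Section 6.1 requires a checklist signed by a physician investigator, with source documents for each item to be verified.

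**The concern.** An exclusion based on unresolved events normally tolerates mild residue and bars anything worse, as item 4 does. The second limb of item 10 bars the mild residue and is silent on anything worse. No evident rationale would exclude the milder patient and admit the sicker one.

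Two things are at stake, both at enrolment. A patient with trivial residual symptoms after a procedure is ineligible on the text. A patient with an unresolved Grade 2 or higher complication may pass every fixed-grade rule and be stopped only if an investigator chooses to stop them.

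The literal wording matters because relief from it is uncertain. Section 17.6 says that the monitoring and scientific review committees no longer accept eligibility deviations, although section 13.3 still mentions eligibility waivers. A site cannot safely act on what it believes the item was meant to say.

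**Working it through.** There is no figure to recompute. The check is one of logic: read the sentence, compare it with the parallel rule, then see whether another criterion fills the gap.

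**Step 1: direction of the limit.** The rule has the form: a participant may not be recovering with events of Grade ≤ 1. A patient who fits the description is excluded; one who does not fit it is not excluded by this limb.

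| Residual event | Item 10, second limb, as written | Item 4 (prior anti-cancer therapy, apart from its exceptions) |
|---|---|---|
| Grade ≤ 1 | excluded | allowed |
| Grade ≥ 2 | not excluded | excluded |

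The two items give opposite answers on each side of the same boundary.

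**Step 2: does another parse rescue it?** The words refer to a procedure related to adverse events, not to procedure-related adverse events, so the phrase is itself garbled. If it means events caused by a procedure, the table above applies. If it means a procedure done because of an adverse event, the limb excludes patients whose event was Grade 1 or lower and is silent on higher grades. The direction is the same either way.

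**Step 3: could the sign be a text-extraction fault?** Inequality signs in both directions appear correctly elsewhere in section 5.2, for example ≤ in item 4 and ≥ in item 23. Nothing suggests that this one was altered.

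**Step 4: do other criteria close the gap at Grade ≥ 2?**

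- Item 10, first limb: only major surgery or significant trauma in the 14 days before treatment.
- Item 4: only events of prior anti-cancer therapy, so a procedure that is not cancer treatment falls outside it.
- Item 18: severe infection within 4 weeks, with conditions on stent function, resolution of infection and a completed antibiotic course after admission for biliary infection at diagnosis.
- Item 23: bleeding only, and only from Grade 3 upward.
- Inclusion 6 (section 5.1): laboratory limits, including liver enzymes and bilirubin, with an exception for obstruction that can be decompressed before therapy.
- Item 33: investigator judgement, with no grade.

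That leaves unresolved Grade ≥ 2 procedure-related events that are neither Grade ≥ 3 bleeding nor severe infection and break no laboratory limit. No fixed rule covers them.

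**Step 5: an illustration.** Take two patients who had major surgery unrelated to cancer treatment 20 days before the first dose, so the 14-day limb is satisfied (20 > 14). One has a residual Grade 1 wound event, the other a residual Grade 2 wound event without infection. Under item 10 as written, the first is excluded and the second is not. Item 4 applies to neither, and items 18 and 23 do not reach the second. Only item 33 could exclude the second.

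**The case against.** The strongest reply is that this is a wording slip with little practical effect. The intended meaning is easy to guess, a physician signs the checklist, registration is verified centrally, and items 18, 23 and 33 already stop many of the worse cases. Most of that stands, and it narrows the gap to the residue in step 4. It does not remove the contradiction: item 33 sets no grade, and central verification works from the criteria as written.

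A reader might go further and infer three stronger things. The documents do not support them.

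- **That pre-existing complications would contaminate the dose-limiting toxicity (DLT) endpoint.** Section 4.1.1.1 requires at least a possible relation to study drug and no clear evidence of another cause. Section 9.4.1.3 treats a condition present at study start as medical history unless it worsens. A complication present before the first dose would largely be kept out.
- **That the observed DLT rate would move by 9 to 17 points.** Those figures are 1/11 = 9% and 1/6 = 17%, from the 6 to 11 patients expected at the maximum tolerated dose (section 4.1.1). They describe any single event in a group of that size, not an effect of this wording. The maximum tolerated dose is estimated from the dose-toxicity model; observed rates are reported alongside it (section 4.1.1.3).
- **That every Phase 1 patient is affected.** Footnote 10 of Table 10 places the screening biopsy "within 14 days of starting therapy but at least three days prior to starting therapy", so recent procedures will be common until ten adequate paired specimens are in hand. That counts procedures, not patients with residual events. Item 10 is also headed as major surgery and trauma, so applying it to a core biopsy is an inference.

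**Conclusion.** The point holds as an error in an operative eligibility rule. The second limb of item 10 points the opposite way to item 4, and no other criterion sets a general limit for unresolved Grade 2 or higher procedure-related events.

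Its size is modest. It bears on who may enrol and on safety at baseline, and it changes no statistical figure in the plan. How many patients it would touch is unknown. The conclusion rests on the plain reading of the sentence and on the ≤ sign being as printed. It does not depend on whether a screening biopsy counts as a procedure under item 10. The correction is worth making because the rule is applied at every enrolment and the remedy is small.

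**What to change.** The sponsor should reconcile item 10 with item 4 and state the second limb without ambiguity. One form that would do so bars procedure-related adverse events that have not resolved to the stated grade. The same edit should replace the garbled phrase about a procedure related to adverse events, and say whether the limb covers procedures other than major surgery, such as the screening biopsy or biliary stenting.

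The study-specific eligibility checklist (section 6.1) and the affiliate-site checklist (section 17.5) should be checked for the same wording. Neither is among the documents, so whether they repeat it is not known.

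The cost is one sentence in a protocol amendment, plus the checklists if they need correcting. The amendment needs review board approval (section 15) and, at affiliate sites, local approval within 90 days of distribution (section 17.2). It can travel with any amendment already in preparation. It needs no change to sample size, analysis or data collection.
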